**Table 4. Combination Nicotine Replacement Therapy (C-NRT) Schedule**

Medication Schedule	Precessation	Cessation	
	TQD -14 to -1	TQD to TQD+7	TQD +8 to TQD+63
	2 weeks	1 week	8 weeks
Medication	No medication		C-NRT (8 weeks)

*Counseling.* Participants will receive counseling at 1 Precessation call and 3 Cessation calls/visits ( $\approx 15$  min, see Table 1-2). Counseling will conform to the US PHS Clinical Practice recommendations for an intensive counseling intervention (motivational, supportive, and skill training elements). Counseling will not explicitly focus on psychoeducation regarding withdrawal symptoms. Counselors will be bachelors-level health educators supervised by licensed psychologists. Quality/fidelity assurance strategies developed by our prior work will include intensive training in counseling techniques and ethical conduct, practice sessions, regular supervision including review of audiotapes, and quarterly team meetings to discuss safety, confidentiality, and counseling fidelity. Participants will be paired with a single counselor whenever possible.

### **Participant Compensation Strategy**

Participants will receive free evidence-based smoking cessation treatment including both counseling and 8 weeks of C-NRT. In addition, participants will be compensated financially for completing study activities and EMA/mobile assessments. Participants will receive \$20 for the Orientation Visit. Participants will receive \$30 for each study visit and \$10 for each telephone call in the Precessation Phase (\$30), and Cessation Phase (\$80). Participants who report abstinence at Call 5 and complete Visit 4 will receive \$50 for this visit. Participants will be compensated for completing  $> 80\%$  of the EMA assessments (\$100). Thus, the total compensation available to participants is \$130 (visits) + \$50 (calls) + \$100 (EMA bonus) = \$280. Importantly, payments will be linked to visit/assessment completion, but not to smoking status so as not to induce participants to incorrectly report their smoking status. This is essential to encourage participants' accurate and honest reporting, particularly as lapse will be an important outcome for evaluating WSWS-2 validity. Compensation will be delivered via checks mailed to participants' residence or distributed at study visits.

### **Analytic Plan**

#### **Specific Aims: WSWS-2 and WSWS-2BR Validation**

Psychometric analyses of the 18 item pool will be conducted to validate a full and brief version (6 items) of the WSWS2 in this sample of medicated and unmedicated smokers. The aims include clarifying the dimensional structure and the best-performing items to construct the final scales. Subscales will be evaluated with respect to internal consistency (e.g., Cronbach's alpha  $\geq .8$ ), item-analysis (response distributions, item-to-total correlations, IRT analyses), and confirmatory factor analyses (CFA) and measurement invariance (e.g., across at least 2 post-TQD time points).

Concurrent, discriminant, and predictive validity will be considered in evaluating and constructing the final scale. The WSWS2-L should demonstrate meaningful relations with measures of tobacco dependence (WISDM-PDM, FTCD, time to first cigarette), other published withdrawal scales (Minnesota Withdrawal Scale), and prediction of cessation outcomes (e.g., time to lapse/relapse, survival analyses). In analyses predicting cessation outcomes both pre-post increase in withdrawal symptoms and post-TQD symptoms per se will be used in prediction models. In addition, such models will be tested with and without (primary) covariates (gender, and race). The WSWS2-L should demonstrate a characteristic time-course of a withdrawal syndrome including sensitivity to abstinence (rise over first 12-24 hours and 2-4 days) and decrease over time following a peak in post-TQD. The time course will be examined with growth curve models that evaluate different trajectory components (i.e., linear, quadratic) with time

varying covariates for smoking lapse occurrence, exposure to temptation events, dependence level. The WSWS2-L should also be sensitive to medication use (e.g., decrease with C-NRT). This will be tested by determining the effects of C-NRT during Cessation on WSWS2-L scores versus precessation and unmedicated cessation levels. The WSWS2-L will be correlated with variables that assess relevant person factors such as affective disorder, distress tolerance, and the various measures of tobacco dependence.

We will conduct parallel set of psychometric and validation analyses of the WSWS2-B as we do with the WSWS2-L, except when not possible due to constraints placed on single-item subscales (e.g., subscale internal consistency, CFA).

### **Exploratory Analyses:**

This study will produce a rich data set for exploratory analyses to both examine the robustness of the primary aims as well as hypothesis generation for future studies. We provide a brief summary of planned theory-driven exploratory analyses, but it is likely that further avenues of analysis will be applied to the data set. We will report all analyses transparently as hypothesis-testing versus exploratory in presentations and published manuscripts. We will examine candidate predictors and moderators of smoking cessation treatment effects in secondary analyses.

Candidate predictors of cessation treatment effects, gathered from EMA and follow-up phone assessments will be: medication use and side effects, withdrawal symptoms (e.g., craving, negative affect), anticipatory pleasure from smoking, adverse events, nicotine reward, nicotine anticipation, and reports of cue-elicited urges. The occurrence of smoking during the quit attempt will be statistically controlled. One-week abstinence will be the primary outcome, which will be modeled via a weighted least squares approach in Mplus. We will attempt to characterize orthogonal routes to outcome change and also examine how certain events such as stressor occurrence or exposure to smoking cues affect withdrawal symptoms via time varying effects modeling.

Analysis of moderators of abstinence outcomes will use both logistic regression with model-fitting techniques and regression tree analyses that reflect differential treatment responses in 1-week abstinence. The logistic regression and regression tree approaches are complementary since the former fits interactions in the entire sample whereas the latter identifies the most robust interactions amongst subpopulations of a sample (groups of participants nested within levels of another predictor, which could include either a covariate or treatment condition). Candidate moderators of treatment effects on abstinence will include tobacco dependence, contextual factors such as household smoking, and biological variables such as sex. In the logistic regression analyses moderators will be evaluated with regards to their interactions with treatment effects.

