## Bio-verification Measures

*Carbon monoxide Assessment.* At all study visits, participants will provide expired breath sample of carbon monoxide (CO; Smokelyzer) for biochemical verification of abstinence. CO is used as both a measure of smoking heaviness at baseline as well as to confirm self-reported abstinence from smoking following the TQD. The higher of two samples recorded will be used as the value for data analysis. A cutoff of  $\leq 5$  ppm will be used as the criteria to be considered abstinent.

*Nicotine/Cotinine Assessment.* At all study visits, participants will provide a urine sample to assess nicotine/cotinine levels, which can be used to estimate smoking heaviness and environmental smoke exposure. Trained study staff at UW-CTRI will collect the participants' urine within the same day. All samples and test results will be labeled with the date of collection and the participant's numerical ID. Urine will be disposed of after nicotine/cotinine levels are read and recorded.

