*Discriminant Validity:*

The WSWS2 subscales should demonstrate weaker relations with measures of an unrelated construct relative to a related/similar construct either measured with the same method (e.g., EMA vs EMA) or different method (e.g., EMA vs. Visit 1 baseline self-report). We will examine Pearson correlations between specific WSWS2-L subscales (e.g., EMA TQD craving, negative affect) and other measures designed to assess unrelated constructs at baseline (e.g., Visit 1 WISDM weight control). Smaller correlations (vs. those observed for convergent validity) will be supportive of discriminant validity for select subscales.

We will conduct similar measures of discriminant validity with the MTWS-R versions.

*Predictive Validity:*

We will examine prospective predictive validity using logistic regression to evaluate if withdrawal severity in the first week post-TQD (via EMA) predicts biochemically confirmed abstinence 1-week post-TQD (Visit 2). The primary outcome is biochemically confirmed ( $\text{CO} \leq 5\text{ppm}$ ) 3d and 24hr point prevalence abstinence (PPA). We will also examine longer-term predictive validity using separate logistic regressions to evaluate if early withdrawal severity (e.g., TQD via EMA, TQD +1-2d Call 4, TQD +1w Visit 2) predicts biochemically confirmed 7-day PPA at end of treatment (>9w Visit 4). For these analyses we will examine both the linear model estimates of TQD jump and post-TQD mean and trajectory (e.g., linear slope, quadratic) as predictors of biochemically confirmed PPA. We will examine predictive validity of post-TQD withdrawal severity both controlling (primary) and not controlling (secondary) for pre-TQD scores as well as controlling for smoking status at time of withdrawal assessment. We will examine the predictive validity of both the WSWS2-L and WSWS-B.

We will also use logistic regression and linear model estimates to examine associations of individual items and subscales of the WSWS2 forms with abstinence outcomes to identify those that are significantly predictive of cessation.

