We assessed specific motives for smoking occasions that were temporally contiguous with craving assessments (e.g., via EMA). Craving is consistently the most informative withdrawal symptom with regard to abstinence prediction and the mediation of smoking treatment effects. Moreover, there are different theoretical accounts of the nature of motives that may underlie or

instigate craving. The various theories yield somewhat different predictions about the subjective states or smoking motives that should be related to craving reports. This research gathered EMA reports assessing smoking motives such as smoking to: reduce distress, to escape nagging thoughts/interrupts regarding smoking, experience the taste/feel of smoking, experience the cigarette high/buzz, enhance pleasure from other activities, and so on. The associations of these items with craving self-report will be examined in order to determine which relatively specific smoking motives are most highly associated with craving in the pre-quit and post-quit periods. This will be done using both zero-order correlations as well as using network analytic methods. Further, the associations of such individual craving items with abstinence onset and smoking status at 1-week post-TQD (Visit 2) and end of treatment (Call 5 & Visit 4) will be determined.

*Sensitivity Analyses:*

We will conduct all psychometric and validation analyses on the maximum available sample at each specified time point as well as on subsets of data to evaluate how the results differ. For instance, we will conduct analyses only on the subset of participants who self-report abstinence at each post-TQD time point as well as with different cut-offs of maximum number of cigarettes smoked per day during each post-TQD period (e.g., <2cpd, <5cpd). We will examine the extent to which results vary as a function of including participants who report complete abstinence versus significant reductions in smoking (and presumably still may be experiencing significant withdrawal symptoms). Likewise, we will examine smoking since the last report as a time-varying covariate in linear models to determine how results vary when controlling for smoking status in this manner.

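### The protocol's exploratory model of one-week abstinence controls for smoking during the quit attempt with no time window, so the covariate overlaps the outcome and lies on the path from the predictors to it

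*Protocol*

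**What the plan says.** The protocol's Exploratory Analyses section describes the work as secondary: "We will examine candidate predictors and moderators of smoking cessation treatment effects in secondary analyses". It names the inputs: "Candidate predictors of cessation treatment effects, gathered from EMA and follow-up phone assessments will be: medication use and side effects, withdrawal symptoms", followed by further items including reward, anticipation and cue-elicited urges. Two consecutive sentences then set up the model: "The occurrence of smoking during the quit attempt will be statistically controlled" and "One-week abstinence will be the primary outcome, which will be modeled via a weighted least squares approach in Mplus".

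The section does not say which days the smoking covariate covers, whether it is any smoking, a count or a time-varying indicator, or which equation it enters. It does not define one-week abstinence either.

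Other sections are more specific, but about other models:

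- Protocol, Bio-verification Measures: "CO is used as both a measure of smoking heaviness at baseline as well as to confirm self-reported abstinence from smoking following the TQD", with a cutoff of 5 ppm or below.
- SAP, Predictive Validity: the one-week outcome at Visit 2 is CO-confirmed "3d and 24hr point prevalence abstinence (PPA"), and withdrawal severity is examined "as well as controlling for smoking status at time of withdrawal assessment".
- SAP, Sensitivity Analyses: "smoking since the last report as a time-varying covariate in linear models".

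The SAP does not restate the Mplus analysis, so the protocol text is the only specification of it.

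**The concern.** The quit attempt begins on the target quit day, so the first week lies inside it. Read as written, the model explains abstinence at one week while holding constant whether the person smoked in that week. This causes two problems.

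First, the covariate shares information with the outcome. Someone who did not smoke at all is, by self-report, abstinent at one week whatever their predictor values.

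Second, smoking lies on the causal path. The SAP's Significance section treats withdrawal severity as a hypothesised driver of lapse. Adjusting for lapse removes the main route by which craving, negative affect or cue-elicited urges would reduce abstinence. The adjusted coefficient then loses its meaning as the predictor's overall relation to abstinence.

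At stake is the interpretation of these exploratory predictor results. A predictor of lapse could look unrelated to abstinence, or a predictor of recovery could look stronger than it is in the whole sample.

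**Working it through.** The documents give no figure for this point, so there is nothing to reproduce. The check is structural, followed by simulation.

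**Notation.** S = 1 if the person smoked at any time in the first week, Y = 1 if abstinent at one week, X = a predictor.

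**Reading A: abstinence means no smoking for seven days.** Then Y = 1 - S exactly. In a probit or logistic model this is perfect separation, and the coefficient of X cannot be estimated. Treating Y as linear would only restate the identity and give no information on X either.

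**Reading B: abstinence means 3-day or 24-hour point prevalence (SAP, Predictive Validity).** By self-report, S = 0 implies Y = 1 for every value of X. Those people do not inform the X coefficient, which is set by

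P(Y=1 | S=1, X) = [P(Y=1 | X) - P(S=0 | X)] / P(S=1 | X).

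This is the probability of recovering after a lapse.

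**Simulation inputs (assumptions, not from the documents).** 400,000 people, seven days, binary X. Where X acts, it adds 0.8 to the daily log odds of smoking. About 75% smoke at least once (74.4%, 74.4% and 75.7% in the three scenarios). Maximum-likelihood probit regression stands in for the Mplus fit. X acts on abstinence only through smoking.

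| X raises | Outcome | No smoking covariate | Any smoking in the week | Smoking on the first four days only |
|---|---|---|---|---|
| lapse start and persistence | 3-day | -0.86 | -0.62 | -0.67 |
| lapse start and persistence | 24-hour | -0.76 | -0.51 | -0.63 |
| lapse start only | 3-day | -0.59 | +0.08 | -0.32 |
| lapse start only | 24-hour | -0.33 | +0.06 | -0.18 |
| persistence only | 3-day | -0.23 | -0.70 | -0.31 |
| persistence only | 24-hour | -0.40 | -0.56 | -0.42 |

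**Hand check, 3-day outcome, persistence only.** Abstinence is 0.357 (X=0) and 0.275 (X=1); never-smoking is 0.243 in both. Unadjusted: probit(0.275) - probit(0.357) = -0.23. Among lapsers: (0.357 - 0.243)/0.757 = 0.151 and (0.275 - 0.243)/0.757 = 0.042. The probit difference is -0.69, against -0.70 from the unrounded fit. The coefficient grows because never-smokers, whom X does not affect here, no longer dilute it.

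**Hand check, 3-day outcome, lapse start only.** Abstinence is 0.435 and 0.227; never-smoking is 0.377 and 0.134. Among lapsers: (0.435 - 0.377)/0.623 = 0.093 and (0.227 - 0.134)/0.866 = 0.107. The difference is +0.08. The sign turns because X=1 lapsers start earlier and have more time to recover before the outcome window.

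**Overlap is partial under Reading B.** Across scenarios, 8-10% of those who smoked in the week were still abstinent on the 3-day definition and 35-40% on the 24-hour definition.

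**At the trial's size.** The SAP's Study Overview gives N = 232. Assume 20-40% never smoke in week one, 10-20% of lapsers recover, and X has a log odds ratio of -0.50 per SD on never smoking.

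- Lapsers: 232 × 0.60 = 139 to 232 × 0.80 = 186. Recovery events: 139 × 0.10 = 14 to 186 × 0.20 = 37.
- No effect on recovery (300 data sets per setting): logistic slopes of -0.27 to -0.45 without the covariate, and -0.01 to 0.01 with it.
- Effect of -0.50 on recovery as well: the adjusted slope stays near -0.50, but its standard deviation across data sets rises from about 0.15 to 0.20-0.34.

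**The case against.** The strongest defence is that the protocol sentence is underspecified rather than wrong. It follows a list of predictors measured by EMA and phone. The protocol's Analytic Plan uses lapse as a time-varying covariate in growth-curve models, and the SAP controls for smoking at the withdrawal assessment or since the last report. A reader could take the sentence to mean the same: adjust the predictor for smoking when it is measured. The outcome's timing is also unclear, because medication use and side effects are listed as predictors although medication starts the day after the one-week visit. This shows that a sensible reading exists. It does not supply one, since the timed covariates belong to other models and no text carries them over to this one.

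A reader might infer something stronger: that the covariate is the outcome itself, and that every predictor acting through smoking will be estimated at zero. The documents do not support that. Exact identity requires abstinence to mean no smoking all week, and then the model is not estimable, which differs from an estimate of zero. Under point prevalence, lapsers can count as abstinent. The zero slope in the N = 232 simulation follows from assuming no effect on recovery; other assumptions give shrinkage or growth. Nor is the cell of non-abstinent never-smokers necessarily empty, because someone reporting no smoking may have a CO above 5 ppm. A non-finite covariate coefficient is therefore conditional.

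It is also fair that a contribution beyond lapse is a legitimate estimand, and that the SAP models the lapse pathway elsewhere, with exploratory survival analyses of time to first lapse and of progression from lapse to regular smoking. Both points lower the weight of the concern. Neither corrects this model.

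**Conclusion.** The concern holds in limited form. Followed as written, the exploratory model adjusts one-week abstinence for a variable that overlaps the outcome and mediates the predictors, with no window to prevent it. If abstinence means a smoke-free week, the model cannot be estimated. Under 3-day or 24-hour point prevalence, the coefficients rest almost entirely on lapsers and describe recovery. They may keep about two thirds to three quarters of their size (67-73%), change sign, or grow up to threefold. They are near zero only for predictors that act on lapse onset alone.

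These sizes depend on the assumed lapse rates and effects, none of which the documents give; the structural point does not. Because the analysis is labelled exploratory and secondary, and the SAP's predictive-validity models are specified separately, priority is low to moderate.

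**What to change.** In the protocol's Exploratory Analyses section, or in a dated addendum to the SAP:

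1. Define one-week abstinence as in the SAP's Predictive Validity section: CO-confirmed 3-day and 24-hour point prevalence at Visit 2.
2. Make the model without the smoking covariate the main one.
3. If smoking is to be controlled, use only smoking before the outcome window opens, or smoking status when the predictor is measured. In the second case, take predictor reports from before the outcome window, because status recorded inside it brings the overlap back. Report this as a secondary model with a different estimand: in the table above, even the early-smoking adjustment moves -0.86 to -0.67 and -0.59 to -0.32.
4. Analyse recovery after a lapse as a separate outcome among lapsers, noting that few events may be available.

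The cost is one or two sentences and one extra model. EMA and timeline follow-back already give timed smoking data, so nothing new need be collected.

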### **Power and Sample Size Justification**

Based on the average expected communalities and the variables-to-factors ratio (factor overdetermination) of the proposed analyses, we believe the sample sizes proposed will provide good power the exploratory factor analyses and other covariance structural modeling (R. C. MacCallum et al., 2001; Robert C. MacCallum et al., 1999). A key prediction concerns the relation between a dichotomized scoring of the WSWS-2B and likelihood of abstinence at follow-up. We propose that those with low withdrawal scores will have an abstinence likelihood

of .40 while those with a high score will have an abstinence likelihood of .20. Assuming  $p=.05$  and  $B=.80$ , the  $N$  for a regression of .20 = 95 (Hsieh et al., 1998). Therefore, we believe the design is adequately powered for the expected results, which would be of clinical significance.

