## **Study Overview**

We propose recruiting up to 500 daily cigarette smokers who report a desire to quit smoking in order to enroll up to 250 participants. This is a treatment-delay, one-group clinical trial that is intended to enhance the assessment of tobacco withdrawal amongst participants who try to quit smoking with delayed use of cessation medication. In addition, it is intended to identify important determinants of withdrawal severity. Participants will not receive any pharmacotherapy during the first 1 week of their quit attempt. They will initiate pharmacotherapy 1 week past the target quit day (TQD) and continue treatment through 9 weeks past the TQD. This will allow for the examination of withdrawal symptoms for 1 week post-TQD in participants who are not using pharmacotherapy. Participants will receive 8 weeks of combination nicotine replacement therapy (C-NRT: nicotine patch + nicotine mini-lozenge) starting 1 week past the TQD. Participants will receive 4 counseling sessions that conform to the US PHS Clinical Practice Guideline recommendations (1 prequit, 3 postquit). Participants will complete 4 weeks of ecological momentary assessment (EMA) including a 2-week baseline (starting TQD-14) and 2-week post-TQD (1-week un-medicated, 1-week using C-NRT). Participants will be recruited via media (newspaper and television advertisements, and Facebook advertisements) to attend an Orientation Visit where the study will be explained and they will provide written informed consent. Once consented, the study will include three phases (described below): Orientation, Precessation and Cessation. Over the 2-week Precessation and the first 2 weeks of the

Cessation phase, participants will complete intensive daily mobile self-report assessment (mobile assessment) of withdrawal and other relevant variables.

*The Orientation Phase.* This will include an Orientation session for all participants and will entail completion of written informed consent, eligibility screening, a self-report assessment battery, and physical assessments (e.g., breath CO, urine nicotine/cotinine levels, blood pressure). Assessments delivered during these visits will include withdrawal assessment, smoking heaviness, use of all nicotine products, and potential mechanisms of treatment (e.g., expectations of smoking reinforcement, smoking contexts, affect). Eligible participants will be scheduled for a Precessation Call.

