## **Participants**

Two hundred participants (age  $\geq 21$ ; 50% women) who smoke  $\geq 5$  cigarettes per day, have a CO level  $\geq 5$  ppm, and report a desire to quit smoking, will be recruited from Madison and Milwaukee, WI. Participants must be willing to attempt to abstain from smoking for 1 week without the use of pharmacotherapy treatment or other nicotine use (e.g., e-cigarettes). See sections below for details on eligibility criteria, recruiting, and participant compensation strategies to enhance retention.

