## Study Overview

Adults who smoked cigarettes daily and desired to quit smoking enrolled in this study (N=232). This treatment-delay, one-group clinical trial was intended to validate and/or enhance the assessment of tobacco withdrawal amongst participants who try to quit smoking without using

medication early in the course of their quit attempt. Participants attempted to quit smoking and were instructed not to use any smoking cessation pharmacotherapy during the first week of their quit attempt. They initiated pharmacotherapy 1 week past the target quit day (TQD) and continued pharmacotherapy through 9 weeks past the TQD. This will allow for the examination of withdrawal symptoms for 1-week post-TQD in participants who are not using pharmacotherapy. Participants received 8 weeks of combination nicotine replacement therapy (C-NRT: nicotine patch + nicotine mini-lozenge) starting 1 week past the TQD. Participants received 4 counseling sessions (1 pre-TQD, 3 post-TQD) that conform to the US PHS Clinical Practice Guideline recommendations (Fiore et al., 2008). Participants completed 4 weeks of ecological momentary assessment (EMA) including a 2-week baseline (starting TQD -14d) and 2-week post-TQD (1-week un-medicated, 1-week using C-NRT). Enrolled participants completed an Orientation Phase, Pre-cessation Phase, Cessation Phase, and Follow-up Phase (Visit 4 only if self-reported 7d point prevalence abstinence). See Tables 1-3 below for timing of assessment and study activities.

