## Data Analysis Plan

### WSWS2 & MTWS-R Scoring:

The WSWS2-L (Smith et al., 2021) is a 19-item scale scored via one total score (mean) and 6 subscale scores (means). The WSWS2-B is a 6-item scale scored as one total score (mean). The WSWS2-L was assessed at all study phone calls and in-person visits (see Table 1-2 for assessment timeline). The brief version (WSWS2-B) was assessed at all EMA reports (3-6x/day), with the exception of TQD -1d through TQD +3d, while the long version (WSWS2-L) was assessed at the evening report (the WSWS2-L comprises the WSWS2-B items). Also see *Exploratory Withdrawal Symptoms* section below.

The MTWS-R is a 17-item scale with one item per symptom domain and no subscales. We will score one total score (mean) of the first 8-items that are DSM-5 symptoms as our primary MTWS-R score. We will score an exploratory MTWS-R including all 17-items (mean) that includes 'other possible symptoms' of smoking withdrawal. The MTWS-R and related information was derived from John Hughes UVM website describing the scale:

<http://www.med.uvm.edu/behaviorandhealth/research/minnesota-tobacco-withdrawal-scale>

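### The stated sample size of 95 does not follow from the dichotomized .40 vs .20 comparison; about 164 (two-sided, even split) are needed

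*Protocol*

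**What the plan says.** The Protocol, Power and Sample Size Justification, gives one numerical power calculation. It opens: "A key prediction concerns the relation between a dichotomized scoring of the WSWS-2B and likelihood of abstinence at follow-up". Low scorers are expected to have an abstinence likelihood "of .40 while those with a high score will have an abstinence likelihood of .20". With p=.05 and B=.80 (read here as alpha and power), it gives the N "for a regression of .20 = 95", cites a paper on sample size for linear and logistic regression, and concludes that "we believe the design is adequately powered for the expected results".

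The section does not say whether the test is one- or two-sided, where the score is cut, what share of participants falls on each side, what the regression of .20 refers to, or how many outcomes may be missing.

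Planned enrollment varies within the Protocol. The Study Overview says "in order to enroll up to 250 participants", the Participants section says "Two hundred participants", and Protection of Human Subjects says at least 250. The SAP, Study Overview, reports 232 enrolled. The SAP scores the WSWS2-B as a mean, and its Predictive Validity section describes no dichotomized analysis.

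**The concern.** Detecting .40 against .20 with 80% power at the 5% level usually takes clearly more than 95 participants in total, so the figure looked too small. It is the only power number in either document, and the adequacy statement is drawn directly from it. If 95 is too low, a reader who compares it with 200 to 250 participants will overestimate how much room there is for an uneven cut-point or for missing outcomes.

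**Working it through.** **Inputs.** From the Protocol's power section: p1=.40, p2=.20, alpha .05, power .80, binary predictor. Sidedness and split are not stated, so I tried both sidednesses and a range of splits. Enrollment figures: 200 and 250 (Protocol), 232 (SAP).

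**Attempt to reproduce 95: two-proportion formula, 50:50.** Per group,

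n = [z_a·√(2·p̄(1−p̄)) + z_b·√(p1(1−p1)+p2(1−p2))]² / (p1−p2)², with p̄=.30.

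- Two-sided: [1.960·√.42 + .842·√.40]²/.04 = (1.270+.532)²/.04 = 81.2, so 82 per group and **164 in total**.
- One-sided: [1.645·√.42 + .842·√.40]²/.04 = (1.066+.532)²/.04 = 63.9, so 64 per group and **128 in total**.

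**Logistic formula with a binary covariate, total N.** With B the share of high scorers and P = (1−B)p1 + B·p2,

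N = [z_a·√(P(1−P)/B) + z_b·√(p1(1−p1) + p2(1−p2)(1−B)/B)]² / [(p1−p2)²(1−B)].

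| High-score share | Two-sided | One-sided |
|---|---|---|
| 50% | 162.4 | 127.7 |
| 75% | 206.2 | 163.4 |
| 25% | 222.5 | 173.8 |

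Over shares from 10% to 90%, the minimum is about 162 two-sided and 128 one-sided. Unpooled, arcsine and Wald variants at 50:50 give 157 to 170 two-sided and 124 to 134 one-sided. A continuity correction raises the totals to 182 and 148. None of these is near 95.

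**What 95 would deliver.** At 50:50, the standard error of the difference is √(.21·4/95)=.0940 under the null and √(.40/47.5)=.0918 under the alternative. Two-sided power is Φ[(.20−1.960·.0940)/.0918] = 57%; one-sided it is 69%. At 80% two-sided power, 95 could detect only about .47 vs .20, or .40 vs .15.

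**Two-sided power at the enrollment figures, full data.**

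| N | 50:50 | 25:75 (either direction) |
|---|---|---|
| 95 | 57% | 42–50% |
| 200 | 88% | 75–79% |
| 232 | 92% | 82–84% |
| 250 | 94% | 85–87% |

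**Margins at 232.**
- Against the stated N: 232/95 = 2.44.
- Two-sided, 50:50: 232/164 = 1.41. One-sided, 50:50: 232/128 = 1.81.
- Two-sided, 25:75: 232/206.2 = 1.13 and 232/222.5 = 1.04.
- Missing outcomes that still leave 80% two-sided power: 1−164/232 = 29% at 50:50; 1−206.2/232 = 11% and 1−222.5/232 = 4% at 25:75.
- With all 232 evaluable, 80% two-sided power holds while the high-score share lies between about 24% and 79%. With 200 the range is about 29% to 74%.

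**Two routes that do land near 95.** Each needs steps the text does not state.
1. *Continuous, normally distributed score.* If the lower half averages .40 and the upper half .20, the log odds ratio per SD is 0.635 in magnitude (odds ratio about 1.89) and the rate at the mean is about .285. Then N = 7.849/[P(1−P)·0.635²], about 93 at P=.30 and 96 at P=.285, where 7.849 = (1.960+.842)². The score is then no longer dichotomized.
2. *Continuity-corrected per-group size, inflated for a correlation of .20.* 90.9/(1−.20²) = 94.7 per group, about 190 in total. The 95 is then not the total N.

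**Continuous score, as the SAP uses it, unadjusted.** The detectable odds ratio per SD is exp√[7.849/(N·P(1−P))]. At N=232 this is 1.49 if overall abstinence is .30 (the midpoint of .40 and .20, an assumption), 1.46 at .40 and 1.58 at .20.

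**The case against.** The strongest reply is that 95 is unexplained rather than shown to be a miscalculation. The sentence contains an undefined quantity (the regression of .20) and relies on a cited method. If 95 was a per-group figure, the plan was asking for about 190, which is more conservative than 164. This stands as a caution about the cause: the documents do not show how 95 arose. It does not rescue the figure, because the text presents 95 as the N for a dichotomized comparison, and for that comparison no split or sidedness brings the total down to 95.

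Second, the conclusion holds at an even split with full data, and at 232 it holds even at 25:75. That is correct. The 25:75 split is a stress case, not something the documents suggest. It matters only because the cut-point is left open.

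Third, enrollment and follow-up are complete, so recalculating power now can look retrospective, and confidence intervals from the fitted models will be more informative. This is fair for power computed from observed effects. Recalculating under the planned .40 and .20 at the evaluable N merely corrects the design statement.

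Fourth, the missing-outcome tolerances are generic. At 9 weeks only participants who report abstinence are invited to Visit 4, so a missing Visit 4 is not a missing outcome for someone who reports smoking. That limits their use at 9 weeks. At Visit 2, however, the Protocol allows a telephone substitute without breath CO, while the SAP's 1-week outcome requires CO confirmation.

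**Conclusion.** The concern holds. As a total for the comparison described, 95 is too low. About 164 are needed two-sided at 50:50, or 128 one-sided, and about 206 to 223 two-sided at 25:75. At 95, power is 57% two-sided or 69% one-sided, not 80%.

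The adequacy conclusion is weakened but not overturned. At an even split with full data, two-sided power is 88% to 94% for 200 to 250 participants. It falls below 80% with 200 participants at 25:75, and it would do so at 232 if more than 4% to 11% of outcomes were missing at that split.

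These results take .40, .20, .05 and .80 as stated; the splits and sidedness are assumptions because the Protocol gives none. Nothing is concluded about power for the SAP's primary predictive model, which adjusts for pre-TQD scores and uses jump, mean and trajectory predictors, because the documents give no correlations from which to compute it.

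**What to change.** In the power section, replace 95 with about 164 evaluable participants, stating a two-sided test and a 50:50 split. Add the power at 232 under the same assumptions (about 92%), and the corresponding figure at the actual evaluable N and split.

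If 95 came from another basis, such as a continuous score with an odds ratio of about 1.89 per SD or a per-group size, state that basis and its assumptions instead, remove the reference to a dichotomized score if it does not apply, and say whether 95 is a total. Either way, explain or delete the regression of .20.

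Because the SAP keeps the score continuous, also report the unadjusted detectable odds ratio per SD: about 1.49 at N=232 with overall abstinence .30 (range 1.46 to 1.58 for abstinence of .40 to .20). Do not carry the adequacy statement over to the adjusted model unless its covariate correlations are given.

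The cost is one corrected number and a few sentences. No participants are added and conduct does not change. The stated margin at 232 becomes 1.4-fold instead of 2.4-fold (two-sided, 50:50).
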